## **Background:**

Atrial fibrillation (AF) is the most common arrhythmia and its prevalence is projected to rise with the increase in age and comorbid disease in the patient population. AF is associated with significant morbidity and a nearly doubled risk of death.

As such the development of therapies which prevent or slow the progression of AF is imperative. In randomized controlled trials of therapies for AF, pharmacologic maintenance of sinus rhythm has not been demonstrated to be superior to therapies to control ventricular rates. In addition, medical therapy to maintain sinus rhythm was associated with significant cost and increased rates of hospitalization . However, in an "on treatment" analysis of the AFFIRM study which originally compared rhythm and rate control strategies, at an average of 3.3 years of follow up, the presence of sinus rhythm was associated with a significantly decreased risk of death (hazard ratio = 0.53). These findings suggest that the adverse effects of antiarrhythmic drugs in rate versus rhythm control studies offset the benefits of maintaining sinus rhythm when they are successful. Catheter ablation of the pulmonary veins and atria has been demonstrated to decrease the frequency of AF by 70-80% in several studies and provides a promising alternative to antiarrhythmic therapies.

Obesity is a known risk factor for AF and weight reduction through caloric reduction and exercise has been demonstrated to decrease the duration and symptomatic burden of AF in overweight and obese individuals in a randomized controlled trial. In a recently published retrospective cohort study of a physician led weight management intervention, successful reduction of 10% of body weight was associated with a six-fold increase in arrhythmia free survival. Similarly, in a cohort study of overweight and obese patients undergoing catheter ablation for AF, a program of aggressive risk factor management prior to ablation led to improved glycemic control, blood pressure reduction, favorable left atrial remodeling and a nearly fivefold increase in AF free survival at two years with less use of antiarrhythmic medications.

Metformin hydrochloride (hereafter referred to as metformin) is the first-line pharmacologic therapy of Type II diabetes and has been associated with modest but sustained weight loss in diabetic individuals . There has not been a randomized controlled trial to assess the weight effect of metformin on non-diabetic individuals who are overweight or obese. However in retrospective studies of metformin use in overweight and obese euglycemic individuals, metformin has been associated with modest weight loss (2.99.0 kg) without evidence of hypoglycemia.  In a placebo controlled randomized controlled trial of metformin therapy of nondiabetic individuals with coronary disease and a large waist circumference, metformin use was associated with a 3.2 kg reduction at 18 months but did not improve other surrogate markers of cardiovascular disease. The known gastrointestinal side effects of metformin therapy occurred with the expected frequency in these studies.

In addition to obesity, there is significant epidemiologic and molecular data which implicates inflammatory, metabolic, and oxidative stress in the development and maintenance of AF. C-Reactive Protein (CRP) levels are known to be elevated in patients with AF and increasing CRP has been demonstrated to correlate with increasing AF burden. Development of AF was associated with a shift from glycolytic to ketolytic metabolism.  In genome wide transcriptional studies, patients susceptible to AF demonstrated decreased expression of sets of genes related to metabolic and oxidative stress responses. 

Metformin acts by decreasing hepatic glucose production and increasing skeletal muscle uptake of blood glucose. These effects are thought to be in part mediated by metformin induced activity of AMP-activated protein kinase (AMPK) alterations in atrial calcium channels. In canine models of atrial fibrillation AMPK activation limits AF promoting In murine models of atrial fibrillation in which liver kinase B1, an activator of AMPK, is deleted, AF develops spontaneously in an age dependent manner and progresses from a paroxysmal to a persistent form in a similar manner to that seen in AF patients. Mutations in PRKAG2 gene, part of a subunit of AMPK have also been associated with early onset AF, and familial conduction diseases including Wolff-Parkinson-White syndromes. In transcriptional studies of human atrial fibrillation, AMPK subunit expression is increased in patients susceptible to AF but who remain in sinus rhythm while AMPK subunit expression is decreased in patients persistently in AF. This further suggests AMPK activity is protective in human AF.

Given the benefits of weight loss in AF, the benefit of metformin for weight loss, and the experimental and genetic evidence linking AMPK activation to metformin therapy and reduction in AF risk, the potential of metformin as an upstream therapy is promising.

### **Trial Objective and Purpose:**

The purpose of this trial is to determine if the upstream use of metformin in patients with atrial fibrillation and obesity undergoing a rhythm control strategy will increase the frequency of maintenance of sinus rhythm at six months. The primary endpoint is the number of patients in normal sinus rhythm after six months of follow up. Secondary endpoints are amount of weight loss, change in BMI, change in hemoglobin A1c, number of thromboembolic events, and burden of atrial fibrillation based on the Atrial Fibrillation Severity Score (AFSS).

#### **Trial Design:**

The proposed study will be a randomized control trial comparing metformin therapy to a control group in patients with a BMI  $\geq$ 27 and atrial fibrillation who have elected to undergo a rhythm control strategy with ablation. Upstream therapy with Metformin will be used in a randomized fashion. The only variation to the standard of care will be the addition of Metformin therapy and additional blood draws for safety monitoring and EKGs for measuring outcomes in both the intervention and control groups.

Patients meeting the below inclusion and exclusion criteria who provide informed consent will be randomized to control versus metformin therapy six weeks prior to rhythm control.

At baseline all study patients will be assessed for:

Age, Gender, Weight, BMI, Tobacco Use, Hypertension, Hemoglobin A1c, Hyperlipidemia, serum CRP, glomerular filtration rate estimating equation (eGFR), B12, liver function tests (AST, ALT, ALP, bilirubin, albumin, INR), lactic acid, History of Coronary Artery Disease by MI, PCI, or CABG, History of Valvular Disease, History of Obstructive Sleep Apnea, Type of AF and duration, Number of Antiarrhythmic Medications (not including beta-blockers or calcium channel blockers).

In addition, patients will fill out a survey to determine their Atrial Fibrillation Severity Score (AFSS) - a validated tool to assess the symptomatic burden of AF - and will receive education on dietary changes and exercise

Metformin will be initiated at 500 mg daily and increased as tolerated to 2000 mg daily over a three week period. Subjects will be instructed to hold Metformin on the day of any procedure or study requiring the administration of intravenous contrast and to resume 48 hours after the contrast administration and reinstituted only after renal function has been reevaluated and found to be at the patient's baseline. All patients will receive information on dietary changes to promote weight loss and will be encouraged to increase exercise activities. Patients will discontinue treatment at any time they are found to meet the baseline exclusion criteria for the study.

The initiation of the drug and the dosage increases will be overseen by a designee (mid-level cardiology practitioner) who will be responsible for stopping dosage increases if side effects occur. Six weeks after the initiation of drug the patient will undergo ablation with the intent of achieving rhythm control.

Patients will be followed up in regular intervals after the initial attempt at rhythm control. The minimum follow up interval is every three months. More frequent follow up may be scheduled as deemed necessary by the treating physician.

[figure not shown]
At the time of the first attempt at rhythm control, at the 3 month follow up, and at the 6 month follow up all study patients will be assessed again for:

Weight, BMI, Hemoglobin A1c, serum CRP, eGFR, liver function tests (AST, ALT, ALP, bilirubin, albumin, INR), B12, lactic acid, number of antiarrhythmic agents, presence of AF by EKG, and Atrial Fibrillation Severity Score.

At each 3-month and 6-month follow up, data will be reviewed by a designee who will use the criteria described below for reporting to the Medical Monitor. The patient will also be assessed for the occurrence of any adverse events as defined below and adverse events will be reported to the medical monitor.

At the end of 6 months of therapy, the decision to continue Metformin beyond 6 months will be made in conjunction with the patient's treating cardiologist and primary care physician.

Figure 1.

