## **Selection and Withdrawal of Subjects:**

Inclusion criteria: All individuals diagnosed with Atrial Fibrillation and choosing to undergo a rhythm control strategy at Robert Packer Hospital with a BMI  $\geq$  27 will be eligible for the study. All subjects must be able to understand and willing to sign a written informed consent document.

Exclusion criteria: Individuals who are already taking metformin or other antidiabetic medications including insulin, have a diagnosis of diabetes, have a known allergy or FDA-labeled contraindication to taking metformin, eGFR below 30 mL/min per 1.73 m^2 or other clinical diagnosis of advanced renal disease,, have acute or chronic metabolic acidosis (serum bicarbonate <22 mEq/L), have a history of significant alcohol use (>2 drinks/day on average), have a history of hepatic dysfunction (serum bilirubin 1.5X greater than the upper limit of normal), have a history of New York Heart Association (NYHA) Class III or IV heart failure, or are pregnant will be excluded from the trial.

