#### **Study Drug Compliance:**

Study drug dispensed to the subjects will be tracked. Subjects will return empty study drug containers and unused study drug at those visits when a new supply of study drug is to be received. Study drug accountability will be performed at each visit. Subjects should report any unintentional interruption or missed doses of 7 consecutive days or more to the study-site personnel at each visit. It is understood that subjects may occasionally miss a dose or that a subject may be placed on temporary discontinuation.

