#### **Outcomes and Assessment of Efficacy:**

The primary outcome by intention to treat analysis will be maintenance of sinus rhythm by chart review, EKG, and Atrial Fibrillation Severity Score at 3 and 6 months after the initial attempt at rhythm control.

Secondary outcomes will include hospitalization related to arrhythmic events or medication side effects, number of antiarrhythmic medications, number of repeat ablations, BMI, Hemoglobin A1c, and number of thromboembolic events.

Pre-specified subgroup comparisons will include comparing patients randomized to metformin who have a 5% reduction in weight at 6 months to all control patients who achieve a 5% reduction in weight, and to all control patients.

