#### **Assessment of Safety:**

A Medical Monitor will be utilized to provide general oversight and safety considerations for this study. The Medical Monitor will provide advice to the Sponsor-Investigator regarding actions the committee deems necessary for the continuing protection of subjects enrolled in this study. The Medical Monitor will be charged with assessing such actions in light of an acceptable risk/benefit profile for metformin. The Medical Monitor will act in an advisory capacity to the Sponsor-Investigator and will monitor subject safety data for the study.

All patients included in the study will have monitoring of renal function, hepatic function, and serum lactic acid at baseline, at the time of ablation or initiation of rhythm control, and at 3-month and 6-month follow ups. This data will be reviewed by an investigator who is not involved in the outcome analysis. This investigator will be a mid-level who will be assigned to check the routine labs. The parameters for immediate reporting to one of the study coordinators are the following- creatinine greater than or equal to 1.5 in males or 1.4 in females, elevated lactic acid, or serum bilirubin >1.5x the upper limit of normal. Exclusion criteria will also be reviewed at each follow up, and if at any point a patient meets the exclusion criteria for the study or has an unexpected adverse event they will be withdrawn from the study.

Routine reports will be provided to the Medical Monitor every 2 months and will include rates of disenrollment, reason for disenrollment, unexpected adverse events, and mortalities. If a statistically significant harm is detected in the analysis of the safety data collected at 2 month intervals the protocol will be terminated.

Adverse events will be solicited at routine follow-up with a designee and are defined as follows: .

Lactic Acidosis – lactic acid >2.1 mmol/L as measured at either routine follow up or if measured during a hospitalization for any reason

Thromboembolic event – any stroke, mesenteric ischemia, limb ischemia, or other event determined to be of an embolic etiology secondary to atrial fibrillation Vitamin B12 levels and any change from baseline at the 3 and 6 month timepoints will be measured and submitted.

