### Potential Risks:

Per the Glucophage (metformin) package insert, metformin does not cause hypoglycemia in individuals with diabetes mellitus or normal subjects except in certain circumstances excluded by the study's exclusion criteria.

Metformin does have a warning for the risk of lactic acidosis. Per the insert:

The reported incidence of lactic acidosis in patients receiving metformin hydrochloride is very low (approximately 0.03 cases/1000 patientyears, with approximately 0.015 fatal cases/1000 patientyears). In more than 20,000 patient-years exposure to metformin in clinical trials, there were no reports of lactic acidosis. Reported cases have occurred primarily in diabetic patients with significant renal insufficiency, including both intrinsic renal disease and renal hypo perfusion, often in the setting of multiple concomitant medical/surgical problems and multiple concomitant medications.

In a more recent review of pooled data from 347 trials and cohort studies an estimated risk of 4.3 cases of lactic acidosis in 100,000 patient years was calculated and this risk was equivalent with other antihyperglycemic agents. The ultimate conclusion of this investigation was "There is no evidence to date that metformin therapy is associated with an increased risk of lactic acidosis or with increased levels of lactate compared with other antihyperglycemic treatments if the drugs are prescribed under study conditions, taking into account contraindications". 26

Other known adverse reactions to metformin therapy include gastrointestinal side effects which include flatulence, diarrhea, nausea and vomiting, and abdominal discomfort. These symptoms are dose dependent and can be relieved by dose reduction. Approximately 50% of all patients can tolerate a maximal dose of metformin but a small minority of around 5% cannot tolerate any dose of metformin.

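### Patients who meet an exclusion criterion or have an unexpected adverse event must leave the study, with no outcome follow-up provided, which undermines the intention-to-treat analysis

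*Combined protocol and SAP*

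**What the plan says.** Two sections apply the exclusion list after randomization, with different consequences.

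- **Trial Design** stops the drug: "Patients will discontinue treatment at any time they are found to meet the baseline exclusion criteria for the study".
- **Assessment of Safety** has the criteria checked again at every follow-up and ends participation: whenever "a patient meets the exclusion criteria for the study or has an unexpected adverse event they will be withdrawn from the study". The two-monthly reports to the Medical Monitor "will include rates of disenrollment, reason for disenrollment, unexpected adverse events, and mortalities".

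The list is in Selection and Withdrawal of Subjects. It begins "Individuals who are already taking metformin or other antidiabetic medications including insulin, have a diagnosis of diabetes" and continues with allergy or labeled contraindication, renal disease, acidosis, alcohol, hepatic dysfunction, NYHA class III or IV heart failure and pregnancy. No item and no arm is exempt from the withdrawal rule.

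Outcomes and Assessment of Efficacy sets the analysis: "The primary outcome by intention to treat analysis will be maintenance of sinus rhythm by chart review, EKG, and Atrial Fibrillation Severity Score". The time points are 3 and 6 months from the first attempt at rhythm control. Among the secondary endpoints, Trial Objective and Purpose states: "Secondary endpoints are amount of weight loss, change in BMI, change in hemoglobin A1c". HbA1c is measured in all patients at the procedure and at both follow-up visits.

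No section says what is collected from a patient after withdrawal. The only allowance for loss is the 3% attrition in Statistics.

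**The concern.** An intention-to-treat analysis needs an outcome for each randomized patient, whatever happened to treatment. A rule that ends participation because of a post-randomization event works against that unless follow-up continues, and here nothing says that it does.

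New diabetes is the clearest example, for three reasons.

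- A control patient has no study drug to stop, so withdrawal protects nobody.
- In the metformin arm the diagnosis alone is no reason to stop, since Background describes metformin as the first-line drug for type II diabetes.
- Potential Benefits says metformin reduces progression from prediabetes to diabetes, so these withdrawals could be more frequent among controls because of the treatment itself. The diagnosis is also related to HbA1c, a secondary endpoint.

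The same sentence withdraws patients for every other exclusion item and for unexpected adverse events, so the defect is wider than diabetes. At stake is whether the patients with outcomes still form a randomized comparison.

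**Working it through.** **1. The rule.** Stopping treatment (Trial Design) leaves follow-up intact. Leaving the study (Assessment of Safety) does not, unless follow-up is provided for. Study Drug Compliance shows that the protocol can separate the two, since "a subject may be placed on temporary discontinuation" while remaining a subject. The withdrawal rule makes no such separation.

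**2. The planned sample size.** Inputs from Statistics: control recurrence p1 = 0.30; 30% relative reduction, so p2 = 0.30 × 0.70 = 0.21; d = 0.09; two-sided 5%; 80% power; 400 per arm including 3% attrition. With p̄ = 0.255:

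n = [1.960·√(2p̄(1−p̄)) + 0.842·√(p1(1−p1) + p2(1−p2))]² / d² = (1.960 × 0.6164 + 0.842 × 0.6131)² / 0.0081 = 367 per arm.

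With continuity correction, n/4·[1 + √(1 + 4/(n·d))]² = 389; then 389/0.97 = 402, close to the stated 400. Without it, 367/0.97 = 379. The plan does not name its formula, but the corrected one fits. On that basis 400 − 389 = 11 patients per arm (2.75%) can be lost, so nothing is spare for protocol-required withdrawals.

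**3. Possible distortion.** The documents give no diabetes incidence or withdrawal rate, so the shares below are assumptions. Let a share w of controls only be withdrawn without an outcome. Observed control recurrence lies between (0.30 − w)/(1 − w), if all of them recurred, and 0.30/(1 − w), if none did. Subtract 0.21 for the difference.

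| w | Control recurrence | Difference (planned 9.0 points) |
|---|---|---|
| 1% | 29.3% to 30.3% | 8.3 to 9.3 |
| 3% | 27.8% to 30.9% | 6.8 to 9.9 |
| 5% | 26.3% to 31.6% | 5.3 to 10.6 |

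These are extreme cases. If withdrawn controls instead had 1.5 times the recurrence risk of those who stay, observed control recurrence is 0.30/(1 + 0.5w) and the differences are 8.9, 8.6 and 8.3 points.

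**4. Power, losing patients against keeping them.** Power = Φ{[d − 1.960·√(p̄(1−p̄)(1/n1 + 1/n2))] / √(p1(1−p1)/n1 + p2(1−p2)/n2)}, with p̄ the pooled rate weighted by arm size. The continuity-corrected version subtracts ½(1/n1 + 1/n2) from d. The starting point is 400 × 0.97 = 388 per arm.

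| Scenario | Uncorrected | Corrected |
|---|---|---|
| 388 vs 388, no further loss | 82.1% | 79.9% |
| 5% of controls lost (388 × 0.95 = 369 vs 388) | 81.2% | 78.9% |
| Those 5% kept, all start metformin with full benefit (p1 = 0.30 − 0.05 × 0.09 = 0.2955; 388 vs 388) | 78.3% | 75.8% |

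Both 5% scenarios change the control arm only, so they are comparable. Keeping the patients costs more power than losing them.

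**The case against.** The strongest reply is that the documents are silent about withdrawn patients rather than in contradiction. Nothing formally removes them from the analysis, intention to treat is declared, and chart review is a named outcome source at what appears to be a single hospital. That stands in part: a reader might infer that withdrawn patients are dropped from the analysis set, and the text does not say so. But it does not say that chart review continues after withdrawal either, and the declared analysis needs those outcomes.

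Other stronger readings also fail.

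- *The Trial Design sentence itself breaches intention to treat.* It only stops treatment, so it does not.
- *The item on already taking metformin would expel the whole metformin arm.* The word refers to entry.
- *The report on disenrollment proves what withdrawal means.* It could equally count voluntary withdrawals.
- *An HbA1c result triggers withdrawal automatically.* The criterion is a diagnosis. No cut-off is set, and HbA1c is not among the immediate-reporting parameters.

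The exposure is also limited: about six weeks before ablation plus the time to the 6-month visit. At that visit the EKG and severity score are scheduled alongside HbA1c, so a diagnosis arising there need not cost the outcome. HbA1c at baseline also gives a chance to notice existing diabetes. All this supports a small effect but does not supply the missing follow-up.

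Finally, stopping metformin can be a safety matter. Potential Risks describes metformin as free of hypoglycemia "except in certain circumstances excluded by the study's exclusion criteria", so a patient who starts insulin loses part of that protection. That is a reason to review the drug, not to end follow-up.

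**Conclusion.** The point holds as a defect in the withdrawal rule under Assessment of Safety: it requires patients in either arm to leave the study for post-randomization events, and no section secures their 3- and 6-month outcomes. This undermines the intention-to-treat analysis without formally contradicting it. New diabetes is the clearest case, not the whole problem.

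The size cannot be determined from the documents and is probably small. The bounds in the working rest on assumed shares, loss in controls only and, at their widest, on all or none of those lost having recurred. Unequal loss between arms is plausible from the protocol's own statement about metformin, but its extent is not shown. The change should be made because it is cheap and protects the randomized comparison; power is not the argument for it.

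**What to change.** **Assessment of Safety.** Replace withdrawal from the study with discontinuation of study drug, for exclusion items and unexpected adverse events alike. Add: *Every patient who has not withdrawn consent keeps the 3- and 6-month assessments and is analyzed as randomized; any antidiabetic drug started is recorded by arm.*

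**Trial Design and Assessment of Safety.** State that a new diabetes diagnosis alone is not a reason to stop study metformin or to leave the study. Starting insulin or another glucose-lowering drug prompts a safety review of study metformin, not study withdrawal. Stopping the drug for the safety items on the list is unaffected.

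**Cost.** A wording amendment, with no visits or tests beyond those already scheduled. The real downside is that controls who start open-label metformin stay in the analysis and dilute the contrast, with the power cost shown in the working. The amendment does not by itself say how outcomes that are still missing will be handled.

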### **Treatment of Subjects:**

At baseline all study patients will be assessed for:

Age, Gender, Weight, BMI, Tobacco Use, Hypertension, Hemoglobin A1c, Hyperlipidemia, serum CRP, eGFR, liver function tests (AST, ALT, ALP, bilirubin, albumin, INR), History of Coronary Artery Disease by MI, PCI, or CABG, History of Valvular Disease, History of Sleep Apnea, Type of AF and duration, Number of Antiarrhythmic Medications (not including beta-blockers or calcium channel blockers).

In addition, patients will fill out a survey to determine their Atrial Fibrillation Severity Score (AFSS) – a validated tool to assess the symptomatic burden of AF - and will receive education on dietary changes and exercise.

Subjects will be randomized to receive either Metformin (500 mg tablet) or into the control group. Subjects will be instructed to take one tablet twice a day with meals. Over a 3 week period, the dosage will be increased to 2000 mg daily (given in a divided dose of 1000 mg twice a day) as tolerated by the patient.

Patients will be followed up in regular intervals after the initial attempt at rhythm control. The minimum follow up interval is every three months. More frequent follow up may be scheduled as deemed necessary by the treating physician.

At the time of the first attempt at rhythm control, at the 3 month follow up, and at the 6 month follow up all study patients will be assessed again for:

Weight, BMI, Hemoglobin A1c, serum CRP, eGFR, liver function tests (AST, ALT, ALP, bilirubin, albumin, INR), number of antiarrhythmic agents, presence of AF by EKG, Atrial Fibrillation Severity Score, occurrence of adverse events.

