#### **Statistics:**

We expect a 30% recurrence of AF after patients undergo ablation. After ablation, we expect the recurrence of AF to be 30% less in the intervention group of patients on metformin than the control group.

Using an 80% power at a 95% confidence interval, the sample size of the control group (ablation only) and the intervention group (ablation plus metformin) will be 400 each for a two tailed study, accounting for up to a 3% attrition rate in each group. The total sample size of this study will be 800. It is estimated to take five years to accrue subjects.

Statistical methods employed to analyze outcomes will be a Pearson's  $X^2$  test for categorical variables. Analysis of Variance will be used for continuous variables. All tests are two-sided and P < .05 will be used to indicate a statistically significant difference.

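### The primary endpoint is sinus rhythm, but the one scheduled rhythm item is presence of AF, and no rule says how atrial flutter, atrial tachycardia or paced rhythm counts

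*Combined protocol and SAP*

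**What the plan says.** All places are in the combined protocol and SAP.

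- **Trial Objective and Purpose:** "The primary endpoint is the number of patients in normal sinus rhythm after six months of follow up".
- **Outcomes and Assessment of Efficacy:** the primary outcome is "maintenance of sinus rhythm by chart review, EKG, and Atrial Fibrillation Severity Score at 3 and 6 months after the initial attempt at rhythm control", analysed by intention to treat.
- **Trial Design, follow-up assessments:** "number of antiarrhythmic agents, presence of AF by EKG, and Atrial Fibrillation Severity Score". **Treatment of Subjects** repeats the item: "number of antiarrhythmic agents, presence of AF by EKG, Atrial Fibrillation Severity Score, occurrence of adverse events". Neither list has an entry for sinus rhythm or for any arrhythmia other than AF.
- **Trial Design, opening paragraph:** both arms have additional "EKGs for measuring outcomes in both the intervention and control groups".
- **Statistics:** "We expect a 30% recurrence of AF after patients undergo ablation". Metformin is expected to lower this by 30%, with 400 patients per arm.

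The body of the protocol does not mention atrial flutter, atrial tachycardia or pacing, and it does not equate absence of AF with sinus rhythm. The only pointer is in the reference list, where one cited paper concerns atrial tachycardia caused by AF ablation. No rate is given.

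**The concern.** The endpoint, the data item and the sample-size event describe three things: being in sinus rhythm, having AF on the EKG, and recurrence of AF. They coincide only if AF and sinus rhythm are the only possibilities. Trial Design has the patients ablated, and the reference list shows that other atrial rhythms after ablation are a known topic.

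For a patient in flutter at six months, a truthful entry in the listed item is that AF is absent. If the analysis uses that item, a failure of rhythm control is counted as a success. If it uses the endpoint wording, the same patient is a failure. The success rate in each arm therefore depends on a choice the plan does not make. No placebo is described for the control arm and nothing is said about concealing the arm from whoever reads the EKG, so that choice could be made with the arm known.

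**Working it through.** **1. Inputs.** From Statistics: 30% AF recurrence in controls; 30% less with metformin, read as relative, so 0.30 × 0.70 = 21%; two-sided alpha 0.05; power 80%; 400 per arm including 3% attrition. Evaluable patients per arm: 400 × 0.97 = 388. An absolute reduction of 30 points would need only about 22 per arm, so the relative reading is the one intended.

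**2. The plan's own figure.** With d = 0.09 and mean proportion 0.255:

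n = [1.960 √(2 × 0.255 × 0.745) + 0.842 √(0.30 × 0.70 + 0.21 × 0.79)]² / 0.09² = 367 per arm.

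With continuity correction, n′ = (n/4)[1 + √(1 + 4/(n d))]² = 389. Allowing for attrition, 389 / 0.97 = 402 after rounding up, against 400 stated. The figure reproduces. The complement, 70% versus 79%, also gives 367 without correction. So sizing on AF recurrence is the same as sizing on sinus rhythm only if no patient has another rhythm.

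**3. Base power with 388 per arm, no continuity correction.**

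Power = Φ[(0.09 × √388 − 1.960 × 0.6164) / 0.6131] = Φ(0.921) = 82.1%.

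**4. Assumption A: failures hidden by the AF item.** Suppose true loss of sinus rhythm is 30% versus 21%, and a share s of failures in each arm is a non-AF rhythm coded as free of AF. Recorded failures become 0.30(1 − s) and 0.21(1 − s). Patients wrongly counted as successes are 388 × 0.30 × s and 388 × 0.21 × s.

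| s | Recorded failures, control vs metformin | Difference (points) | Wrong successes, control / metformin | Power |
|---|---|---|---|---|
| 0 | 30.0% vs 21.0% | 9.0 | 0 / 0 | 82.1% |
| 5% | 28.5% vs 19.95% | 8.55 | 6 / 4 | 79.5% |
| 10% | 27.0% vs 18.9% | 8.1 | 12 / 8 | 76.6% |
| 20% | 24.0% vs 16.8% | 7.2 | 23 / 16 | 70.2% |
| 30% | 21.0% vs 14.7% | 6.3 | 35 / 24 | 63.0% |

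The relative risk stays at 0.70 in every row. The absolute difference and the power fall.

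**5. Assumption B: these rhythms come on top of AF and metformin does not affect them.** AF is 30% versus 21%, and a further f of each arm is in flutter or tachycardia and is correctly counted as failure. The difference stays at 9 points but the variance rises. Power is 80.3% at f = 2%, 77.8% at 5% and 74.6% at 10%.

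**6. Assumption C: as B, but metformin lowers these rhythms by the same 30%.** Power rises to 85.3% at f = 2% and 89.4% at 5%.

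The documents give no basis for choosing among A, B and C, nor for any value of s or f.

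**The case against.** The strongest reply is that the visit lists are summaries, not the definition of the endpoint. Outcomes and Assessment of Efficacy names chart review and the EKG as sources, and Trial Design says the extra EKGs are there to measure outcomes. Either source can show flutter, and no case report form is in the documents to prove otherwise. This stands in part. A reader might infer that the plan counts flutter as success, or that the endpoint cannot be obtained at all. The documents support neither. By the endpoint wording flutter is a failure, and the tracing will exist.

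What the reply does not supply is a rule. Three sources are named with no order among them. The protocol itself describes AFSS as a measure of symptom burden, so it cannot identify a rhythm, and chart review has no stated rhythm criteria. Assessment of Safety keeps the reviewer of safety laboratory results apart from the outcome analysis; nothing similar is said for EKG reading.

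Two further inferences should be resisted:

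- The word normal in the objective might be read as failing a patient with sinus bradycardia. That is strained: no rate criterion appears anywhere, and the efficacy section says only sinus rhythm.
- One might set the number of patients per arm in these rhythms (at 5%, 388 × 0.05 = 19) against the planned difference of 388 × 0.09 = 35 patients. One is a count within an arm and the other a difference between arms. If 5% of each arm is in flutter whatever the treatment, the gap is 9 points either way: 30% versus 21% for AF, 35% versus 26% for any of these rhythms.

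**Conclusion.** The point holds as a mismatch between endpoint, scheduled data item and sample-size event, together with a missing rule for non-AF, non-sinus rhythms. It is not an arithmetic error, and the sample size reproduces.

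The size depends on a rate the documents do not give. Under assumption A the effect is small if such rhythms are rare (79.5% power when 5% of failures are hidden) and material if they are common (70.2% at 20%). With an equal share hidden in both arms, the relative risk is not biased. An unequal share, which unconcealed reading would permit, could bias the comparison in either direction; the documents offer nothing to size that.

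The case for change does not rest on power, since correct coding can lower power (assumption B) or raise it (assumption C). It rests on measuring the stated endpoint, in the same way in both arms, from EKGs already planned. This should be settled before outcomes are classified.

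**What to change.** 1. In the follow-up lists under Trial Design and Treatment of Subjects, replace the AF item with the rhythm on EKG: sinus (any rate), AF, atrial flutter, atrial tachycardia, paced, other.
2. In Trial Objective and Purpose and in Outcomes and Assessment of Efficacy, define success as sinus rhythm at any rate on the visit EKG, and AF, flutter or atrial tachycardia as failure. State how paced and other rhythms count.
3. State that the EKG decides the rhythm and that AFSS, a symptom score, does not. Say what part, if any, chart review plays.
4. Name who reads the study EKGs (no reader is described at present) and have them classify the tracings without knowing the arm.
5. In Statistics, restate the expected event as loss of sinus rhythm under this definition and recheck the 400 per arm. Report AF alone as a supportive analysis.

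The cost is one changed data field, some wording and an arrangement for concealed reading; no extra EKGs are needed. The success rate will be slightly lower than with AF alone. If flutter and tachycardia are unaffected by metformin, power falls from 82.1% to 80.3% at 2% per arm or 77.8% at 5%, and the restated sample size should acknowledge this.
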